8.2.3 Immunophenotyping on lymph nodes using EBUS-FACS analysis

Absolute values of the individual immune cells will be calculated for TDLNs and NTDLNs.

The percentage difference between TDLNs, NTDLNs, peripheral blood and immune cells isolates from the resection specimen will be calculated and values will be quantified on a linear scale and compared within each patient (postinduction vs baseline) and between the treatment arms (SBRT vs SBRT + pembrolizumab) with the use of the paired t-test and the independent samples t-test, respectively.

8.3 Analysis of PET data

SUV_{max} , SUV_{mean} and SUV_{peak} will be measured in all tumor lesions, enlarged lymph nodes and liver, kidneys, lungs, spleen and left ventricle of the heart.

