3.2 Secondary Objectives & Hypotheses

Objective 1:

To assess uptake (visual and quantitatively, expressed as SUV_{max} , SUV_{mean} and SUV_{peak}) of radiolabeled pembrolizumab (^{89}Zr -pembrolizumab) in the tumor and lymph nodes by use of PET.

Hypothesis 1:

^{89}Zr -pembrolizumab tumor uptake heterogeneity between patients is expected and can be visualized. We expect that the level of ^{89}Zr -Pembrolizumab uptake will be related to the immunohistological results (immune effector subsets with special interest to the expression of PD-1 and PD-L1) of the whole tumor as well as regional tumor areas.

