4.0 BACKGROUND & RATIONALE

4.1 Background

4.1.1 Stereotactic body radiotherapy for the treatment of early stage NSCLC

The current standard treatment for early stage NSCLC is an anatomical surgical resection, with SBRT being reserved for patients not fit to undergo resection. Despite the early stage of disease, 5-year overall survival after surgical resection is only 45-50% due to locoregional as well as distant relapse (1). Although none of the planned randomized studies of surgery versus SBRT have completed accrual, a pooled analysis of our ROSEL study together with the STARS trial from MD Anderson has been published (2). Estimated overall survival at 3 years was 95% (95% CI 85-100) in the SBRT group compared with 79% (64-97) in the surgery group (hazard ratio [HR] 0.14 [95% CI 0.017-1.190], log-rank p=0.037). Recurrence-free survival at 3 years was 86% (95% CI 74-100) in the SBRT group and 80% (95% CI 65-97) in the surgery group (HR 0.69 [95% CI 0.21-2.29], log-rank p=0.54).

This was a very surprising finding because the main presumed advantage of surgery over SBRT is the ipsilateral hilar and mediastinal lymph node dissection with unexpected lymph node (micro)metastases found in 15% of patients (3). The unexpectedly good results with SBRT may be caused by an immunological response against tumor cells, triggered by the radiotherapy. High dose radiation has been shown to induce an antitumor immune response mediated by T-cell regulation, both in the primary tumor and the TDLNs (4, 5). However, despite the promising results of SBRT and this exciting biological mechanism, overall survival was not different between the two modalities in this study. In another study, 676 patients underwent SBRT for early stage lung cancer with a 2-year recurrence rate of 22% and a median overall survival of 41 months (6). Furthermore, of the 124 recurrences, 82 (66%) were distant recurrences.

These results clearly reveal that disease recurrence rates still remain substantial with both modalities, despite their curative intent.

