 - Correlate the 3D ⁸⁹Zr-pembrolizumab PET image results with the 3D primary tumor histopathology results and the lymph node histopathology results.
- In the lobectomy specimen the tumor surrounding healthy tissue will be examined for radiation induced changes.

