5.1.2 Subject Inclusion Criteria

In order to be eligible for participation in this trial, the subject must:

1. Have a histologically or cytologically confirmed diagnosis of early stage (T1bN0 and T2aN0) peripherally located NCSLC, eligible for surgical resection.
2. Be willing and able to provide written informed consent/assent for the trial.
3. Be ≥ 18 years of age on day of signing informed consent.
4. Have measurable disease based on RECIST 1.1.

5. Must provide tissue from a core or excisional biopsy of the primary tumor lesion.
6. Have a performance status of 0-1 on the ECOG Performance Scale.
7. Demonstrate adequate organ function as defined in Table 1, all screening labs should be performed within 10 days of treatment initiation.

Table 1. Adequate Organ Function Laboratory Values

System	Laboratory Value
Hematological	
Absolute neutrophil count (ANC)	≥1,500 /mcL
Platelets	≥100,000 / mcL
Hemoglobin	≥9 g/dL or ≥5.6 mmol/L
Renal	
Serum creatinine OR Measured or calculated creatinine clearance (GFR can also be used in place of creatinine or CrCl)	≤1.5 X upper limit of normal (ULN) OR ≥45 mL/min for subject with creatinine levels > 1.5 X institutional ULN
Hepatic	
Serum total bilirubin	≤ 1.5 X ULN OR Direct bilirubin ≤ ULN for subjects with total bilirubin levels > 1.5 ULN
AST (SGOT) and ALT (SGPT)	≤ 2.5 X ULN OR ≤ 5 X ULN for subjects with liver metastases

8. Female subject of childbearing potential should have a negative urine or serum pregnancy within 72 hours prior to receiving the first dose of study medication. If the urine test is positive or cannot be confirmed as negative, a serum pregnancy test will be required.
9. Female subjects of childbearing potential should be willing to use 2 methods of birth control or be surgically sterile, or abstain from heterosexual activity for the course of the study through 120 days after the last dose of study medication. Subjects of childbearing potential are those who have not been surgically sterilized or have not been free from menses for > 1 year.
10. Male subjects should agree to use an adequate method of contraception starting with the first dose of study therapy through 120 days after the last dose of study therapy.

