5.3.2.6 Analysis of PET data

Tumor volumes of interest will be delineated using semi-automated in-house developed software. SUV_{max} , SUV_{mean} and SUV_{peak} will be calculated for the tumor and visible lymph nodes (67-69).

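### Node SUV is limited to *visible* nodes in section 5.3.2.6 and *enlarged* nodes in section 8.3: two undefined, different rules that do not follow the nodes actually sampled, with no node analysis in section 8.5

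*Combined protocol and SAP*

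**What the plan says.** Secondary objective 1 (section 3.2) is to assess tracer uptake, visually and by SUV, "in the tumor and lymph nodes by use of PET". It sets no condition on node size or visibility. Section 4.2.3 adds an aim to correlate the tracer images with the "3D primary tumor histopathology results and the lymph node histopathology results". Section 4.2.4 makes the correlation of immuno-PET with tissue and blood immune parameters the secondary endpoint.

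Two sections say which nodes get an SUV:

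- Section 5.3.2.6: the three SUVs "will be calculated for the tumor and visible lymph nodes".
- Section 8.3: they "will be measured in all tumor lesions, enlarged lymph nodes and liver, kidneys, lungs, spleen and left ventricle of the heart".

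No size cut-off is given for *enlarged*, and section 5.3.2.6 does not say whether *visible* means on CT or on the tracer image.

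The inclusion criterion (section 5.1.2) is a "diagnosis of early stage (T1bN0 and T2aN0) peripherally located NCSLC". Section 5.5.1 aspirates hilar and mediastinal nodes by EBUS, and section 5.6.3 makes nodal sampling at resection mandatory. Both choose nodes by location and set no size or uptake condition.

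**The concern.** The PET side and the tissue side of the node question choose their nodes differently. Tissue comes from anatomical stations. SUV comes only from nodes that are enlarged or visible, depending on which section the analyst follows. Two analysts could build different node datasets from the same scans.

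The choice matters for this tracer. It binds PD-1, which section 4.1.2 describes as expressed on activated lymphocytes, so a normal-sized node is a relevant target. Hypothesis 2 in section 3.1 expects immune changes in tumor-draining nodes in this same N0 population. A rule based on enlargement leaves out normal-sized nodes that have been sampled.

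At stake is the node part of a secondary objective. It could rest on few, selected nodes with no stated way of linking them to the flow-cytometry results, although scans and aspirates both exist.

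**Working it through.** **1. Scanned patients.** The plan's own figure is 20 patients, 10 per arm (section 5.2); 2 × 10 = 20. There is no formal power calculation, so there is nothing further to reproduce. Section 4.2.3 and the flow chart (section 6.1) give the tracer to the pembrolizumab arm only. Section 5.3.2.5 speaks of all patients having two scans; read with those sections, that means all who receive the tracer. The ceiling is about 10 patients, with scans at 72 h and 144 h: 10 × 2 = 20 scans.

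**2. How many might contribute under the *enlarged* rule.** Let p be the share of patients with at least one enlarged node. The documents do not give p. Their only nodal rate is "unexpected lymph node (micro)metastases found in 15% of patients" (section 4.1.1), which concerns occult disease, not node size, and cannot stand in for p. With n = 10, the expected number of contributors is 10p and the chance of none is (1 − p)^10:

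| Assumed p | Expected contributors | Chance of none |
|---|---|---|
| 0.05 | 0.5 | 0.60 |
| 0.10 | 1.0 | 0.35 |
| 0.20 | 2.0 | 0.11 |
| 0.30 | 3.0 | 0.03 |
| 0.50 | 5.0 | 0.001 |
| 0.80 | 8.0 | <0.001 |

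At 10–30% this is 1–3 of 10. The upper rows of the range matter as much: if p is 0.5 or more, scarcity is no longer the main problem.

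**3. What that means for a correlation** (two-sided 5%, an assumption). The smallest significant |r| is t/√(n − 2 + t²), with t the 97.5% point on n − 2 degrees of freedom.

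- n = 3: 12.706/√(1 + 161.4) = 0.997
- n = 5: 0.88
- n = 10: 2.306/√(8 + 5.32) = 0.63

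With all 10 patients, an observed r of 0.5 has a Fisher-z 95% interval of tanh(0.549 ± 1.96/√7) = −0.19 to 0.86. Full inclusion still gives a wide estimate.

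**4. Measured nodes against sampled nodes.** Under section 8.3, a sampled node of normal size has no SUV. Nothing would be lost only if every sampled node happened to be enlarged. Under section 5.3.2.6 the loss depends on what *visible* means: a tracer reading drops low-uptake nodes, and a CT reading drops far less.

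**5. Link and analysis.** Section 7.1.2.7.2 describes PET-to-pathology matching for the primary tumor only; resected nodes are scraped and sent to flow cytometry. Section 8.2.1 confines IHC to the primary tumor. Section 8.5 relates SUV to tissue PD-1 and PD-L1 IHC and to blood variables. Section 8.2.3 analyses EBUS flow data without SUV. So no section pairs node SUV with a node result.

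**6. Timing.** In the flow chart the tracer scan and baseline EBUS share the day −14 to 0 window. Resection is at days 56–70, after SBRT and pembrolizumab.

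**The case against.** A restriction to larger or visible nodes can be defended as a measurement choice. Resolution is about 7 mm (section 5.3.2.5). Section 8.3.1 acknowledges partial-volume and motion effects and says that acquisition is not respiratory gated. Small nodes will give low-biased SUVs, and some hilar nodes may be hard to place on a low-dose CT. This stands. It is a reason to report node diameter and to restrict recording to stations that can be located, but it does not justify two undefined rules.

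The hypothesis attached to the objective concerns the tumor only ("tumor uptake heterogeneity between patients is expected and can be visualized"), and the objective also allows visual assessment, so a node without signal still yields a result. The trial is exploratory. These points also stand and limit the consequence.

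Several stronger readings are tempting but unsupported:

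- *Most patients will contribute no node SUV.* No document gives the rate. N0 is a metastatic stage, not a node size, and a tracer-visible rule could admit most of the 10.
- *Visible nodes enter because uptake is high, which inflates mean node uptake.* This holds only if *visible* means tracer-visible. Section 5.3.2.5 defines regions on co-registered CT, and no mean node uptake is a planned estimate.
- *Node SUV cannot be paired with tissue.* A measured node may also be a sampled one. What is missing is a written link.
- *The node part of the objective cannot be answered.* It is under-specified, but visual and some quantitative data will exist.

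**Conclusion.** The point holds as a design weakness worth correcting. It does not threaten the trial. From the documents alone: the two node rules differ and are undefined; they select on size or visibility while tissue sampling goes by location; at most about 10 patients are scanned; and section 8.5 contains no station-level link or node analysis. It follows that some nodes with tissue data will have no SUV.

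That node data may be few is conditional. The figure of 1–3 patients out of 10 rests on an assumed 10–30% with an enlarged node and on section 8.3 being the governing rule. The correction removes the selection and supplies the link. It does not lift the cap of about 10 patients, so the node result remains an estimate with a wide interval.

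**What to change.** 1. In sections 5.3.2.6 and 8.3, replace *visible* and *enlarged* with one rule. For each hilar or mediastinal station sampled at the baseline EBUS that can be located on the co-registered CT, record SUVmax, SUVmean and SUVpeak at 72 h and 144 h, whatever the node's size or uptake and including values at background. State how many sampled stations could not be located.
2. Report node diameter with every value, so that partial-volume-limited SUVs can be identified. Section 7.1.2.7.2 puts the SUVpeak region at roughly 1 cm, so in smaller nodes it will reach beyond the node.
3. In section 8.5, add a descriptive station-level comparison of node SUV with the baseline EBUS flow-cytometry result for the same station. Stations within a patient are not independent, so give the number of patients as well as stations, and present estimates with intervals, not tests.
4. Treat any comparison of pretreatment SUV with resected nodes as secondary, and label it as confounded by the treatment given in between.

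The cost is SAP wording and extra region drawing on about 20 existing scans, with no added procedure or radiation. The downside is that SUVs in small nodes are biased low and must be read alongside node size.

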8.3.1 Heterogeneity analysis

8.3.1.1 Interpatient heterogeneity

Test-retest variability of PET using modern machines is ~15% (79-81). Therefore, uptake difference between patients (interpatient heterogeneity) is defined as SUV differences of 15% or greater.

8.3.1.2 Inpatient heterogeneity

Tracer uptake differences between lesions of the same patient depend on multiple aspects. These are both biological (e.g. the level of perfusion and target expression), as well as technical (e.g. partial volume and tumor motion effects). True biological differences between lesions that correlate with tumor biology are therefore difficult to define. Therefore, inpatient ^{89}Zr -pembrolizumab uptake differences will be assessed qualitatively.

8.3.1.3 Intratumor heterogeneity

Uptake heterogeneity within a tumor also depends on multiple aspects. It can be the result of biological differences, such as perfusion (the tracer is not able to reach some parts of the tumor), true target expression or tumor necrosis. Tumor motion effects also influence intratumor heterogeneity since PET acquisition is not respiratory gated. Intratumor heterogeneity is defined as the ratio of $SUV_{peak} : SUV_{mean}$. The level will be calculated on a linear scale.

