5.3.2.4 Blood sample analysis

Blood samples (7 mL) will be withdrawn at 10 min post-injection, 72 hours and 144 hours post-injection of ^{89}Zr -pembrolizumab to determine ^{89}Zr -kinetics based on measurements of radioactivity.

5.3.2.5 ^{89}Zr -pembrolizumab PET procedure

All PET scans will be performed on a Philips Ingenuity TF PET/CT scanner.

All patients will undergo two whole body PET scans at $t = 72$ and $t = 144$ hours post-injection. The PET scans will be preceded by a 30 mAs low-dose CT, used for attenuation correction and anatomical localization of the PET-signal. Following CT, a total body PET scan will be acquired. PET scans consist of 10-12 bed positions, depending on the length of the patient, of 5 minutes each. Total acquisition time per scan, including low dose CT will be around 60 minutes.

PET data will be normalized and corrected for randoms, tissue attenuation, decay, scatter and dead time. PET-CT data will be reconstructed with TF-OSEM, resulting in a transaxial spatial resolution of ~ 7 mm in the centre of the field of view. Regions of interest (ROIs) will be defined using the CT images which are co-registered to the PET-CT data. ROIs around the organs which accumulate ^{89}Zr (e.g. liver, lung and other metastatic lesions) will be drawn manually directly on the PET images. All tissue concentrations will be related to the blood concentration (venous samples). The radioactivity concentrations in all regions for all imaging time points will be recorded digitally in a spread sheet.

Quantitative accuracy of ^{89}Zr -PET scans was previously confirmed in our center using phantom studies and comparisons between PET-derived and biopsy tumor radioactivity concentrations (64, 65).

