7.1.2.7.2 Post-resection specimen

Primary tumor

After resection, the resection specimen will be marked intraoperatively by the surgeon. To enable PET and pathology correlation, the resected specimen and the PET/CT scan are carefully inspected and tissue samples analyzed from the appropriate area of the specimen, according to institutional protocol (75). Margins of specimens will be inked, formalin fixed and sectioned into approximately 1 cm thick slices. Photographs of serial sections will be made. Subsequently, several tissue blocks will be sampled and embedded in paraffin. This facilitates orientation and localization of anatomical structures corresponding to different parts of the tumor on the PET/CT scans. Histological sections of the formalin fixed paraffin embedded blocks from the resected specimens will be examined blinded for the PET data. An estimation of the visually assessed vital tumor percentage will be given for the whole of the tumor. Multiple slides taken from all tumor segments (approximately 1 cm² each) will be scored by the same IHC panel as for the baseline biopsy, which is then used for comparison with SUV values. The presence of tumor cells that may influence the uptake of FDG will also be determined. All IHC parameters will be scored semi-quantitatively (absent = 0, few = 1, moderate = 2, extensive = 3). Tumor segment areas were evaluated per 1 cm², as this approximates the PET resolution and the dimension of the spherical ROI used to determine SUV_{peak}.

Lymph nodes

Immune cells will be isolated from the hilar and mediastinal lymph nodes in the resection specimen by the use of a cytologic scraping method as previously described (60). In short, lymph nodes will be bisected lengthwise with a surgical scalpel. From one half, 10 scrapes are made with a surgical blade (no. 22). The scrape material will be phenotypically analyzed by flow cytometry as described in section 5.5.2.

Tumor surrounding normal lobar lung tissue

The tumor surrounding non-tumor lobar lung tissue will be examined for radiation induced (fibrotic) changes. The percentage of fibrosis and immune cell infiltrate surrounding the tumor will be assessed semi-quantitatively (absent = 0, few = 1, moderate = 2, extensive = 3) (75).

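### The SUVpeak:SUVmean index of intratumor heterogeneity is confounded by tumor size and by an unstated volume rule: a perfectly uniform tumor scores roughly 1.1 to 1.4, not 1

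*Combined protocol and SAP*

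**What the plan says.** Section 8.3.1.3: "Intratumor heterogeneity is defined as the ratio of" SUVpeak to SUVmean, calculated on a linear scale. The section names perfusion, target expression, necrosis and ungated breathing motion as influences. It does not mention partial volume, and it gives no reference value, cutoff or size adjustment.

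Section 8.3.1.2, on differences between lesions of one patient, does list causes that are "technical (e.g. partial volume and tumor motion effects", and for that reason assesses those differences only qualitatively.

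Section 5.3.2.5 says the images are processed "resulting in a transaxial spatial resolution of ~ 7 mm in the centre of the field of view". Section 7.1.2.7.2 samples pathology in areas of 1 cm², "as this approximates the PET resolution and the dimension of the spherical ROI used to determine" SUVpeak, so the peak region is a sphere of about 1 cm.

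On the volume behind SUVmean the plan is not specific. Section 5.3.2.5 states: "Regions of interest (ROIs) will be defined using the CT images which are co-registered to the PET-CT data". Section 5.3.2.6 states: "Tumor volumes of interest will be delineated using semi-automated in-house developed software". Neither says whether the tumor volume follows the CT edge or a percentage of maximum uptake.

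**The concern.** SUVpeak is read from a small sphere at the hottest, least blurred place. SUVmean is taken over the whole volume, including a rim that loses signal to its surroundings. The rim is a larger share of a small tumor than of a large one. The ratio therefore exceeds 1 without any biological heterogeneity, by an amount that changes with diameter, background and the rule that draws the volume.

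Section 4.2.5 makes heterogeneity of uptake within individual tumors an explicit hypothesis. A reader who takes 1 as the value for a uniform tumor would see support for it in a uniform lesion, and could rank a small uniform tumor level with a larger, genuinely uneven one. The tracer scan is confined to the combination arm, about 10 patients, so adjusting for size later by modelling would be weak.

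**Working it through.** The plan gives no value for this index, so there is none to reproduce. The check asks what a uniform tumor would score.

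**Inputs from the documents.** Resolution about 7 mm (5.3.2.5); peak region a sphere of about 1 cm (7.1.2.7.2); index SUVpeak/SUVmean (8.3.1.3).

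**Assumptions.** Blur is an isotropic Gaussian of 7 mm full width at half maximum. The peak sphere is 1 mL, so its diameter is (6 × 1000/π)^(1/3) = 12.4 mm. Tumors are spheres of 20 to 50 mm; the plan gives stages ("early stage (T1bN0 and T2aN0) peripherally located NCSLC, eligible for surgical resection") but no range of diameters. Background and volume rule are varied because the plan states neither.

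**Formula.** Blur a sphere of uptake 1 in zero background. Let P be the mean in the peak sphere and M the mean inside the true edge. The ratio is P/M. With background b as a fraction of tumor uptake it becomes [b + (1−b)P] / [b + (1−b)M].

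| Diameter (mm) | P | M | True edge, b = 0 | True edge, b = 0.25 | 41% of max, b = 0 | 50% of max, b = 0 |
|---|---|---|---|---|---|---|
| 20 | 0.897 | 0.652 | 1.38 | 1.25 | 1.33 | 1.23 |
| 25 | 0.983 | 0.718 | 1.37 | 1.25 | 1.37 | 1.27 |
| 30 | 0.998 | 0.764 | 1.31 | 1.21 | 1.31 | 1.24 |
| 40 | 1.000 | 0.822 | 1.22 | 1.15 | 1.24 | 1.18 |
| 50 | 1.000 | 0.857 | 1.17 | 1.12 | 1.19 | 1.14 |

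Example at 25 mm and b = 0.25: (0.25 + 0.75 × 0.983) / (0.25 + 0.75 × 0.718) = 0.987/0.789 = 1.25.

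Further settings, over 20 to 50 mm:
- True edge, b = 0.5: 1.15 down to 1.08.
- 70% threshold, b = 0: 1.13 down to 1.07.
- 41% threshold, b = 0.25: up to 1.44; at b = 0.33: up to about 1.5.
- 10 mm of motion, true edge, b = 0: 1.39 down to 1.20.

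Every uniform 20 to 50 mm sphere scored above 1. Most settings fall between 1.1 and 1.4.

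**Size against real heterogeneity** (b = 0, true edge). Give half of a 50 mm tumor 70% uptake. By symmetry the mean is 0.857 × 0.85 = 0.728; the peak stays at 0.999; the ratio is 1.37 (1.36 to 1.38, depending on how the grid treats the dividing plane). The uniform 25 mm tumor also scores 1.37.

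With half at 50% uptake the mean is 0.75 × M. At 30 mm: 0.930/0.573 = 1.62, against 1.31 uniform. At 50 mm: 0.999/0.643 = 1.55, against 1.17. At 20 mm the gain is smaller: 1.48 against 1.38. Size alone moves the uniform value by at most 1.38 − 1.17 = 0.21.

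**Threshold volumes** (b = 0). At 30 mm, half at 50% uptake moves the index from 1.31 to 1.43 (41% rule) or from 1.24 to 1.30 (50% rule), gains of 0.12 and 0.06. Size moves it by 1.37 − 1.19 = 0.18 and 1.27 − 1.14 = 0.13. At 20 mm under the 50% rule that heterogeneity lowers the index, from 1.23 to 1.17.

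**Cold core** (inner half of the diameter at 20% uptake; true edge, b = 0). At 30 mm the index is 1.08 against 1.31 for uniform. At 50 mm it is 1.18 against 1.17, so the reversal depends on size.

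**The case against.** A reader might go further and infer that the index largely measures tumor size. The documents do not support that. With a true-edge volume, marked one-sided heterogeneity adds about 0.3 to 0.4 at 30 to 50 mm (1.62 − 1.31; 1.55 − 1.17), against at most 0.21 from size. Only with threshold volumes is the size effect comparable or larger. The plan does not say which rule applies, and its reference to CT-defined regions leans towards the anatomical edge. The true spread of heterogeneity between patients is also unknown.

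Nor would every patient be labelled heterogeneous. Section 8.3.1.3 sets no cutoff and does not say that 1 means uniform.

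It is also tempting to set the size gap against the 15% in section 8.3.1.1. With no background the gap between 25 and 50 mm is 1.37/1.17, or 17%; at 25% background it is 1.25/1.12, or 12%. That 15% is in any case a test-retest figure applied to SUV differences between patients, not to this ratio.

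Finally, no test uses the index: sections 8.5 and 8.6 work with SUV. Intratumor heterogeneity is also studied by segment-level pathology matched to PET (7.1.2.7.2), and section 8.3.1.3 does disclose motion.

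These points limit the consequence. They do not supply the missing reference value or volume rule.

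**Conclusion.** The concern holds in a limited form. At the stated resolution SUVpeak:SUVmean is not 1 for a uniform tumor. It is roughly 1.1 to 1.4 for 2 to 5 cm, generally higher for smaller tumors, and it shifts with background and with a contouring rule that the plan leaves open. It can rate a small uniform tumor level with a larger uneven one, and it can fall when there is a cold core. Section 8.3.1.2 recognises partial volume; section 8.3.1.3 does not account for it.

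The range rests on spherical tumors, Gaussian blur, a 1 mL peak sphere and the assumed diameters. Dominance of size over biology is not shown. The index is descriptive, untested and part of a secondary imaging aim, so this is a worthwhile low-cost improvement and no threat to the primary endpoints.

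**What to change.** In section 8.3.1.3, and to match in 5.3.2.6:

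- Fix one volume rule for SUVmean in all patients, for example the CT-defined contour.
- Beside each raw ratio, report CT tumor volume and the ratio expected for a uniform tumor of the same contour, blurred at scanner resolution (7 mm or the center's phantom value) and with that patient's measured surrounding background included.
- Interpret the ratio as a departure from that reference in either direction, not as distance from 1. A value below the reference suggests a cold core.

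The background term is needed. If the reference is built without it, a uniform tumor at 25% background gives 1.25/1.38 = 0.91 at 20 mm and 1.12/1.17 = 0.96 at 50 mm, which is still size-dependent and not 1.

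The cost is a little image processing on existing scans and a few lines of SAP text, with no added procedure for patients. Residual motion blur and dependence on the background estimate should be stated as caveats.
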